# 7.2.1 The ECG study:

The ECG computer analysis study will collect periodic data from the ILR during sinus rhythm and during episodes of AF (both patient-activated and automatic sampling). Patients in the ILR group will be encouraged to make a monthly patient-activated sampling after five minutes of rest (most likely in sinus rhythm). Standard 12-lead ECGs will be obtained at baseline (ILR and control groups) and also annually in the ILR group. ECG markers predictive of future AF will be derived from the recordings. Objectives:

Primary: To study the the association between chronological developments of ECG markers measured by ILRs and incident AF, in order to identify which patients fall into low or high risk AF groups.

Secondary: Calculation of daily AF burden (ILR group) to refine quantification of episodes beyond merely presence/absence and to guide decisions regarding the need for anticoagulation. Relationship between AF burden and development of ECG markers.

#### Additional ECG studies:

- Incidence rate and timing of new onset AF to identify the necessary duration and regularity of ECG monitoring to reliably identify change in status.
- Throughout the ECG study we will also monitor the frequency of symptom triggered ILR transmissions, the proportion of falsely detected AF episodes by ILR as well as the number of planned ECG samplings and data transmissions from ILR devices which are not received.
- Bradyarrhythmia and ventricular tachyarrhytmia.

# 7.2.2 The health economic study:

The health economic analysis is appended to the analysis of the randomized clinical trial.

# Objectives:

Analysis of changes in the use of healthcare resources and costs, i.e. hospital treatment, general practitioner services, medical specialists, pharmaceuticals, rehabilitation, and nursing homes, and analysis of quality-adjusted life-years (QALYs).

#### Comments:

Individual personal data on resource use and health outcomes will be collected prospectively during the trial or from national registers, which also continuously record healthcare consumption. The framework for the analysis is a cost-utility analysis where the mean differences in costs and QALYs between the intervention and the control group is expressed as a ratio that shows the cost per QALY gained from the introduction of ILR monitoring and subsequently AF management. All costs will be estimated from a societal perspective.

Resource use data in relation to the implantation of ILR, ILR data transmission and analysis, as well as follow-up visits, will be recorded prospectively. The registration will include noting the amount of time staff spend during pre-operative evaluation, procedures (e.g. blood tests, electrocardiogram), utensils, anaesthetics, sedatives, antibiotics and hospital stay for each participant. In order to estimate costs, information about salaries, the cost of utensils, pharmaceuticals and equipment will be collected from the hospital finance department.

Data on the participants' use of inpatient and outpatient hospital care and use of emergency departments, general practitioners and other private practising medical specialists, physiotherapists, chiropractors, chiropodists and psychological counsellors, as well as prescription drugs, will be collected from the National Patient Register, the National Insurance Service Register, and the Register of Medicinal Product Statistics. It is assumed that costs of healthcare consumption unaffected by the intervention will cancel out due to randomization. Furthermore, it is assumed that all AF management costs will be captured in the register data.

Hospital treatment will be valued with official hospital charges (diagnosis related group (DRG) charges) provided by the National Board of Health. Special attention to the relevance of using DRG charges will be considered. Services from private practising providers will be valued according to the prevailing fee schedules that are agreed upon between the providers and the regional health authorities. For the valuation of general practitioner services an annual amount will be added to take into account that general practitioners are paid by a combination of capitation and fee-for-service. Furthermore, patients' co-payments will be added. Data on the participants' use of prescription drugs will be collected from the Register of Medicinal Product Statistics. These drugs will be valued according to the pharmacy sales prices.

Information about the participants' use of services provided by the municipalities, e.g. community nurse visits, personal care and practical assistance at home, nursing home, respite care and rehabilitation, will be collected from the participants' municipality of residence. Unit costs of these

services will be estimated based on statistics on wage rates and databases that record the cost of providing home care, (e.g. The Free Choice Database (*Fritvalgsdatabasen*)), which is administered by the National Board of Social Services. All costs will be converted to a specific year price level using the consumer price index and other relevant price indices.

QALYs will be estimated with the use of the EQ-5D-5L instrument. Participants will fill in the EQ-5D-5L questionnaire at baseline (before operation) and every second year (mailed to control group). Each health state is converted to a social tariff (utility score) from a representative sample of the Danish population. This will be used to construct each participant's utility profile. A straight line relation between each of the observed utility scores will be assumed. The number of QALYs experienced by each participant will be calculated as the area under the participant's utility profile.

Descriptive analyses will be used to describe the mean QALYs, resource use and costs per participant in both arms of the trial. Differences in QALYs, resource use and costs between the two groups after 24 months of the study will be based on the trial data. Confidence intervals of 95% for differences between the two groups will be computed based on bootstrap re-sampling with 5,000 replications of the trial data.

For the cost-effectiveness analyses, the incremental cost-effectiveness ration (ICER) will be estimated on the basis of the mean difference in costs relative to the mean difference in

QALYs. Uncertainty about the ICERs will be analysed using bootstrapping and presented in a cost-effectiveness plane. A cost-effectiveness acceptability curve will be generated to represent the probability that ILRs are cost-effective compared with usual treatment. Estimates of the costs per QALY gained from ILR will be compared to similar estimates of rehabilitation after stroke, AF management as well as other cost-effectiveness estimates in other treatment areas.

Study nurses will register all contacts between study subject and study nurse in the hospital files to be included in the cost evaluation.

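### Adjusting the 24-month cost comparison for register costs before randomisation would be an inexpensive, optional gain in precision

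*Protocol*

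**What the plan says.** Section 7.2.2 of the protocol (Comments) sets out the cost-utility analysis in some detail.

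- **Sources.** Data on resource use and health outcomes are "collected prospectively during the trial or from national registers, which also continuously record healthcare consumption". Hospital, practitioner and prescription data come from "the National Patient Register, the National Insurance Service Register, and the Register of Medicinal Product Statistics". Data on home care, nursing homes and rehabilitation "will be collected from the participants' municipality of residence". Resource use for ILR implantation and follow-up is recorded in the trial.
- **Unrelated cost.** "It is assumed that costs of healthcare consumption unaffected by the intervention will cancel out due to randomization".
- **Horizon.** "Differences in QALYs, resource use and costs between the two groups after 24 months of the study will be based on the trial data".
- **Interval.** "Confidence intervals of 95% for differences between the two groups will be computed based on bootstrap re-sampling with 5,000 replications of the trial data".
- **Cost per QALY.** The ratio "will be estimated on the basis of the mean difference in costs relative to the mean difference in" QALYs.

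No covariate is named for the cost difference. Elsewhere the protocol does name baseline adjustment: section 10.6.2.2 uses the baseline score as a covariate for quality of life, and section 10.6.2.1 plans a covariate-adjusted supportive analysis of the primary endpoint.

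**The concern.** Costs that screening does not affect have the same expected value in both arms. In the one trial that is run they do not vanish: each subject's unrelated hospital, practitioner and drug costs stay in the total and add to its variance. Subjects are 70 to 90 years old with at least one chronic condition, so such costs may be large, although the protocol gives no figure for them.

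Prior cost usually predicts later cost to some degree, and part of that variance can then be removed by adjustment. If the registers already hold prior cost, leaving it out gives a wider interval for the cost difference than the data would allow. That difference is the numerator of the cost-effectiveness ratio and feeds the cost-effectiveness plane and acceptability curve. Cost-effectiveness is secondary hypothesis b in section 2.5.2, and the expected results in section 1 are meant to inform health policy.

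**Working it through.** The protocol gives no cost SD, expected cost difference, cost precision or correlation between prior and in-trial cost. It therefore has no cost figure to reproduce, and results are in SD units or over a stated range of assumptions.

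**Inputs**
- Arm sizes: 1,500 ILR and 4,500 control (synopsis, Sample size).
- r: the within-arm correlation between register cost before randomisation and total 24-month cost. Assumption, 0.2 to 0.7.
- s: (value per QALY x SD of QALYs) / SD of costs. Assumption, 0.25 to 2.

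**Step 1. Unadjusted standard error**

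SE = SD x sqrt(1/1,500 + 1/4,500) = SD x sqrt(0.000889) = 0.0298 SD.

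The 95% half-width is 1.96 x 0.0298 = 0.058 SD.

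**Step 2. Adjusted standard error**

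With prior cost as a linear covariate, SE is multiplied by sqrt(1 - r^2). The sample size that would give the same precision without adjustment is 6,000 / (1 - r^2).

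| Assumed r | sqrt(1 - r^2) | Fall in SE | Equivalent N |
|---|---|---|---|
| 0.2 | 0.980 | 2.0% | 6,250 |
| 0.3 | 0.954 | 4.6% | 6,593 |
| 0.5 | 0.866 | 13.4% | 8,000 |
| 0.7 | 0.714 | 28.6% | 11,765 |

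**Step 3. Does this hold for skewed costs?**

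A simulation with log-normal costs, 1,500 against 4,500 subjects and 1,500 runs gave raw-scale correlations of about 0.25, 0.43 and 0.68. The ratio of adjusted to unadjusted SE was 0.97, 0.89 and 0.73, against 0.97, 0.90 and 0.74 from the formula. Both estimators were essentially unbiased.

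**Step 4. Carry-over to cost-effectiveness**

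Net benefit combines the cost difference with a valued QALY difference. If costs and QALYs are taken as uncorrelated, and prior cost explains cost only, its SE is multiplied by sqrt((1 - r^2 + s^2) / (1 + s^2)). At r = 0.5:

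- s = 0.25: sqrt(0.8125 / 1.0625) = 0.874, a fall of 12.6%.
- s = 1: sqrt(1.75 / 2) = 0.935, a fall of 6.5%.
- s = 2: sqrt(4.75 / 5) = 0.975, a fall of 2.5%.

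**Step 5. Scale in money (illustration)**

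If the SD of 24-month cost is DKK 100,000 to 200,000 (assumption), the unadjusted half-width is 0.0584 x SD, about DKK 5,800 to 11,700. The Funding section values 900 devices at DKK 5.4 million at the reduced price, or 5,400,000 / 900 = DKK 6,000 each. Under that assumption the interval extends about one to two devices' cost either side of the estimate, so precision is worth having. At r = 0.5 the half-width becomes about DKK 5,100 to 10,100 (multiply by 0.866).

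**The case against.** The strongest reply is that nothing here is wrong. In context, the cancellation sentence explains why all-cause register cost can be used without separating AF-related care. It concerns bias, and on bias it is correct. An adjusted estimator relies on randomisation in the same way. The text says mean difference, which does not exclude an adjusted one, and covariates for a supplementary cost model are often left to a statistical analysis plan, which was not available here. Health economic cost is a supplementary endpoint (section 10.2.4). The size of the gain rests wholly on a correlation that the protocol does not give.

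Most of this stands. It rules out three stronger readings that a reader might infer:

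- **That the comparison is biased or the assumption false.** It is not; the unadjusted difference is unbiased.
- **That chance differences in prior illness would pass unnoticed as a cost or saving of screening.** The bootstrap interval already carries chance imbalance as sampling uncertainty.
- **That the gain in the cost difference passes in full to cost per QALY.** It does not; QALY variance dilutes it (step 4).

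Two limits on the covariate also stand. That the registers hold costs before randomisation is a fair inference from continuous recording, but it is not stated. Nor do the registers cover everything: municipal care comes from another source, and ILR costs have no counterpart before randomisation.

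What the reply does not remove is that section 7.2.2 already fixes the horizon, the type of estimate, the interval method and the number of replications, and gives cancellation as its only treatment of unrelated cost. A more precise estimator is within reach at that same level of detail.

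**Conclusion.** The point holds as forgone precision in the cost difference. It is not a bias, an error or a contradiction, and the stated analysis would remain valid if left unchanged. The gain is about 2% of the SE at r = 0.2, 5% at r = 0.3 and 13% at r = 0.5, and less for net benefit or cost per QALY. These figures rest on an assumed correlation and on the registers reaching back before randomisation. At the low end the change hardly matters; at moderate correlation it is worth having. It is best treated as an optional improvement to a supplementary analysis.

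**What to change.** In section 7.2.2 or the statistical analysis plan:

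1. Keep the cancellation sentence, and add that it holds in expectation and that unrelated costs still contribute variance.
2. Prespecify the cost difference adjusted for each subject's register cost in the 12 months before randomisation. State that the covariate excludes municipal and ILR costs, while the outcome remains total cost.
3. Refit the adjustment in each of the 5,000 bootstrap samples, resampling each subject's costs and QALYs together.
4. Report the unadjusted difference alongside.

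The cost is some wording, a register extract that starts one year earlier (its availability should be confirmed first) and slightly more analysis work. No extra visits or subjects are needed. Fixing the covariate in advance also avoids a choice made after the cost data have been seen.

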- Assessment of QoL and cognitive function: At randomization, months 12, 24 and 36.
- Vital signs (BP, HR ...): At randomization and at (12, 24), 36 months.
- 12-lead ECG: At randomization and at (12, 24), 36 months.
- Concomitant therapy: At randomization and months 12, 24, 36 and by lookup in medical records and registries at least on a yearly basis.
- Remote Loop Recorder readings: Daily
- Adverse events (AEs): At clinical visits and by lookup in medical records and registries at least on a yearly basis (see section 9 for definitions).

Information on all AEs, that occur from study day 1 after randomization will be recorded in the appropriate eCRFs on study visits and by lookup in medical records and registries at least on a yearly basis. All serious adverse events (SAEs) will be reported to the study office within one working day of discovery (see appendix C), and a SAE form must be completed (see section 9.3 for definitions). Bleeding complications will be registered according to the suggestions by the International Society for Thrombosis and Haemostasis (Schulman and Kearon, 2005). For the efficacy analysis of mortality, the endpoint committee (EC) will review all deaths and classify the events as cardiovascular or non-cardiovascular (see Appendix J). Cardiovascular deaths will be further classified as sudden and non-

sudden based on a time criteria (see Appendix J). Adjudicated cause of death as well investigatorreported cause of death will be entered into the eCRF.

A subgroup of those patients that underwent an echocardiography at inclusion will be invited to participate in a similar echocardiography during follow-up. The criteria for invitation is that the participants should have been included in the LOOP study before January 2017 at one of the study centres Rigshospitalet, Bispebjerg Hospital or Roskilde Hospital, and that the first echocardiography should be between 2 and 6 years old at the time of follow-up echocardiography.

For endpoints, see section 10.2

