# 10.6.2.2 Secondary Endpoints:

See section 10.2.2.

For the time-to-event variables, analysis similar to the one employed for the primary endpoint will be used. The censoring mechanism will also be similar to the one used for the analysis of the primary endpoint. The secondary endpoints will be tested at a significance level of 0.05. Within the first two secondary endpoints the type 1 error rate associated with a multiplicity of comparisons will be controlled according to the Hochberg adjustment. The Quality of Life endpoint will be tested at the 5% significance level. Quality of Life score will be analysed as repeated measures analysis of covariance mixed effects model using baseline score as a covariate.

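### Baseline EQ-5D-5L is a component of every QALY, yet section 7.2.2 names no baseline adjustment for the QALY difference; adding it is an optional, low-cost gain in precision

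*Protocol*

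**What the plan says.** Section 7.2.2 (The health economic study, Comments) sets out the QALY calculation in steps.

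- Timing: "Participants will fill in the EQ-5D-5L questionnaire at baseline (before operation) and every second year (mailed to control group").
- Interpolation: "A straight line relation between each of the observed utility scores will be assumed".
- Summary per participant: "The number of QALYs experienced by each participant will be calculated as the area under the participant's utility profile".
- Comparison: "Differences in QALYs, resource use and costs between the two groups after 24 months of the study will be based on the trial data", with 95% intervals "computed based on bootstrap re-sampling with 5,000 replications of the trial data".
- The ICER is "estimated on the basis of the mean difference in costs relative to the mean difference in" QALYs. The cost-effectiveness plane and acceptability curve follow from it.

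No step mentions baseline utility as a covariate. For the quality-of-life score, section 10.6.2.2 does: "Quality of Life score will be analysed as repeated measures analysis of covariance mixed effects model using baseline score as a covariate".

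Section 7.2.1 (The main study) gives a different timing: "Assessment of QoL and cognitive function: At randomization, months 12, 24 and 36". Appendix A also shows quality-of-life assessment at each of the three follow-up visits in both arms. Neither place says which instrument is meant, so whether EQ-5D-5L is taken yearly or two-yearly is unclear.

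**The concern.** The baseline score is measured before any intervention, so screening cannot change it, yet it is part of the outcome being compared. If the arms differ at baseline by chance, that difference passes straight into the QALY difference, and through it into the ICER denominator, the plane and the acceptability curve. A bootstrap of plain means reports this variation but does not remove it.

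These outputs address secondary hypothesis 2.5.2b, on cost-effectiveness. The expected QALY gain over 24 months is small, so an avoidable source of noise matters more here than it would for a large effect. The value needed to remove it is already planned for collection at baseline.

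**Working it through.** The protocol gives no SD, correlation, standard error or power for utilities, so there is no figure of its own to reproduce.

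**Inputs from the protocol:** 1,500 and 4,500 participants (synopsis), a 24-month horizon and straight-line interpolation (7.2.2), the two schedules (7.2.2 and 7.2.1), and a control rate of 1% per year with hazard ratio 0.65 (10.3).

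**Assumptions, not in the protocol:** utility SD 0.15 to 0.20, equal over time; correlation ρ between any two scores of 0.3 to 0.7; mean utility 0.85; mortality 2 to 4% per year, unrelated to baseline utility; utility 0 after death.

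**1. Weight of baseline, for survivors**

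- Two-yearly: QALY = 2 × (u0 + u24)/2 = u0 + u24. Baseline has 1 of 2 units of weight, 50%.
- Yearly: QALY = 0.5·u0 + u12 + 0.5·u24. Baseline has 0.5 of 2 units, 25%.

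**2. Chance baseline imbalance**

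SE of the baseline difference = SD × √(1/1500 + 1/4500) = SD × 0.0298, which is 0.0045 at SD 0.15 and 0.0060 at SD 0.20.

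Through the direct weight alone, a one-SE imbalance moves the QALY difference by 0.0045 to 0.0060 (two-yearly) or 0.0022 to 0.0030 (yearly). Later scores correlate with baseline, so the full shift on the two-yearly schedule is (1 + ρ) times the imbalance. At ρ = 0.5 and SD 0.15 that is 1.5 × 0.00447 = 0.0067. With deaths at 2% and 4% per year it is 0.0066 and 0.0065, almost unchanged.

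**3. Ratio of unadjusted to adjusted SE, ignoring deaths**

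Ratio = √[Var(Q) / (Var(Q) − Cov(Q,u0)²)], in units of SD².

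- Two-yearly: Var = 2 + 2ρ and Cov = 1 + ρ, so the ratio is √(2/(1 − ρ)): 1.69, 2.00 and 2.58 at ρ = 0.3, 0.5 and 0.7.
- Yearly: Var = 1.5 + 2.5ρ and Cov = 0.5 + 1.5ρ. At ρ = 0.5, √(2.75/(2.75 − 1.5625)) = 1.52. At 0.3 and 0.7 it is 1.29 and 1.96.

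At ρ = 0.5 the SE of the QALY difference falls from 0.0077–0.0103 to 0.0039–0.0052 (two-yearly), or from 0.0074–0.0099 to 0.0049–0.0065 (yearly).

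**4. The same ratio with deaths, by simulation (SD 0.15 to 0.20, ρ 0.3 to 0.7)**

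| Assumed mortality per year | Two-yearly | Yearly |
|---|---|---|
| none | 1.69–2.58 | 1.29–1.96 |
| 2% | 1.28–1.70 | 1.14–1.51 |
| 4% | 1.18–1.47 | 1.09–1.36 |

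Deaths add QALY variation that baseline utility does not explain in this model, so the ratio shrinks to about 1.1 to 1.7.

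**5. Scale against the expected gain**

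The design rates differ by 1.0% − 0.65% = 0.35% per year, or 0.007 strokes per participant over two years. At an assumed utility loss of 0.2 to 0.3 for about one year, that is 0.0014 to 0.0021 QALY. Even the adjusted SEs in step 3, which ignore deaths, run from 0.0039/0.0021 = 1.9 to 0.0065/0.0014 = 4.6 times that gain. The chance that the estimate has the right sign moves from Φ(0.0014/0.0103) to Φ(0.0021/0.0074), about 55–61%, up to Φ(0.0014/0.0065) to Φ(0.0021/0.0039), about 59–71%.

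Section 5.4 gives 1:9 allocation where the rest of the protocol gives 1:3. The ratios in steps 3 and 4 do not depend on allocation. At 600 and 5,400 the factor in step 2 would be 0.0430.

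**The case against.** The case for leaving the text alone has five parts.

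- **The plan may already adjust.** The protocol never calls the difference raw or unadjusted, and a regression-adjusted difference is also a mean difference. Covariates for an economic evaluation are often set in an analysis plan, and none is shown here. This stands as a limit: a reader might infer that the protocol prescribes an unadjusted comparison, but it only names no adjustment. Section 7.2.2 does nevertheless specify the estimator step by step, and the protocol says so elsewhere when it intends adjustment.
- **Nothing is biased.** A reader might infer that baseline imbalance distorts the cost per QALY systematically. It does not: randomisation makes the simple difference unbiased, and the bootstrap interval already includes chance baseline variation. This stands in full. What is lost is precision, and protection against the imbalance that happens to occur.
- **Section 10.6.2.2 is not a contradiction.** It covers a separate test of the quality-of-life score. Section 10.2.4 also lists change from baseline in quality of life together with QALYs, although that wording is ambiguous. This stands too; the comparison shows only that the data and the practice are already in the protocol.
- **The gain is modest and does not rescue the analysis.** A reader might infer from the no-death figures that the SE would halve, or that adjustment would give good power for QALYs. Participants are aged 70 to 90, so ignoring deaths is not realistic, and step 5 shows that chance still largely decides the sign after adjustment.
- **The effect on the decision is not shown.** Adjusting QALYs leaves cost variance untouched, and no effect on the ICER interval or acceptability curve has been calculated.

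None of these points favours the plain difference over the adjusted one.

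**Conclusion.** The point holds as an optional improvement, not as an error. As written, the QALY comparison is valid but less precise than the planned data allow, and it leaves the ICER denominator open to a chance baseline difference whose SE is about 0.0045 to 0.006 in utility. The unadjusted SE is about 1.1 to 1.7 times the adjusted SE under 2 to 4% yearly mortality; 1.3 to 2.6 times applies only if deaths are ignored and both schedules are pooled. All of these sizes rest on the assumed SD, correlations and mortality. If baseline utility also predicts death, the gain would be somewhat larger than the simulation shows.

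QALYs and costs are supplementary endpoints (section 10.2.4). The primary and secondary endpoints, the event target and the error rates are unaffected. The unclear EQ-5D-5L timing needs settling in any case, because it changes how the QALY is calculated.

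**What to change.** In section 7.2.2, state that the QALY difference is the group coefficient from a regression of QALYs on randomised group and baseline EQ-5D-5L utility. Refit the regression in each of the 5,000 bootstrap replicates, resampling each participant's costs and QALYs together. Use that difference in the ICER, the plane and the acceptability curve, and show raw means by arm descriptively. If an analysis plan already specifies this, bring section 7.2.2 into line with it.

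Reconcile the two-yearly schedule in section 7.2.2 with the yearly one in section 7.2.1 and Appendix A, and say which instrument each refers to.

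The cost is a sentence or two of text and one regression in the bootstrap code, with no new data or visits. The one drawback is that participants without a baseline EQ-5D-5L need a simple imputation, which should be stated in advance. Fixing the method now also prevents a choice between adjusted and unadjusted results once they are known.

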# **Study Duration:**

The study comprises an inclusion period of approximately 2 years followed by at intervention phase of minimum 3 years. The total study duration will therefore be approximately 5 years.

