# 10. STATISTICAL CONSIDERATIONS:

# 10.1 Study Design:

This is a prospective randomized, open-label (unblinded), controlled, parallel group multi-center study performed in Denmark. Patients are recruited following identification from Danish registries as well as from outpatient clinics, and after hospitalizations. The study will recruit individuals who live in the Capital Region of Denmark, Region Zealand or the Southern Region of Denmark. The study is expected to conclude when 279 strokes have occurred or 6,000 study subjects have been followed for at least 36 months, which is expected to be approximately 5 years after enrolment of the first subject. Subjects meeting the eligibility criteria will be randomized to either receive an ILR (ILR group) or not ie, continue standard care (control group). The randomization occurs at a ratio of 1:3 (ILR group vs.

control group) as described in section 5.2. The LOOP study will comply with the standards of the CONSORT Statement. The study design is further described in section 3.

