#### Appendix E – Device information: the Medtronic Reveal® LINQ:

In this study the Medtronic Reveal® LINQ insertable, cardiac monitor is used. The Reveal® LINQ is the newest and smallest ILR on the market which is expected to be market released by February 2014. It has battery longevity of three years and additionally 12 months of shelf life. Its size is 1.19 cc which is about 10% of the previous model (Medtronic Reveal® LINQ which has a volume of 9 cc). In contrast to the XT model the LINQ model has a build-in antenna which enables automatic remote transmissions. The device has an event memory of a total of 57 minutes (which is longer than the memory of the XT model: 49.5 minutes) (128 Hz) with up to 30 events in total. The total memory capacity is divided into 22.5 minutes of patient activated events (with the three most recent manual events lasting 7.5 minutes each), and additionally 27 minutes auto-activated events. The device is magnetic resonance (MR) conditional, which means that the Reveal® is safe for use in MR environments. Due to the algorithm the device uses for AF detection it will only categorize an arrhythmia event as atrial fibrillation, if it lasts more than two minutes in total. The arrhythmia detection capabilities of the Reveal® LINQ categorize arrhythmias into 5 groups: Fast VT, VT, bradycardia, asystolia, and AT/AF. The Reveal® LINQ Recorder is prepared for CareLink remote monitoring, with both automated daily transmissions and patient activated transmissions. The device can record AT/AF burden, heart rate variability, day versus night frequency and patient activity. Prior to implant it is recommended to check the vector of the device, with the purpose of finding the orientation with optimal R wave amplitude via the programmer. The device is supplied with a so-called patient assistant, which is a patient activating device. The device algorithm for atrial fibrillation detection is based on measurement of the RR-intervals and the delta RR-interval (change in RR interval from the preceding RR interval), which is afterwards visually presented in a so-called Lorenz plot (cluster signature matrix), where normal sinus rhythm or atrial flutter will be shown as a highly concentrated black spot in the center of the plot, whereas atrial fibrillation will be widely distributed in the cluster signature matrix ("gunshot profile").

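### Section 7.2.2 fixes the cost and QALY comparison at 24 months without a reason, although a third year is planned and scheduled, and its EQ-5D-5L timing conflicts with the visit schedule

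*Protocol*

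**What the plan says.** The protocol's health economic section (7.2.2) sets the time point of the comparison: "Differences in QALYs, resource use and costs between the two groups after 24 months of the study will be based on the trial data". The ICER then "will be estimated on the basis of the mean difference in costs relative to the mean difference in" QALYs. The section names no 36-month, end-of-study or modelled horizon and does not explain the choice of 24 months.

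Other parts of the protocol run longer:

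- Synopsis, Study Duration: "The study comprises an inclusion period of approximately 2 years followed by at intervention phase of minimum 3 years".
- Section 10.1: the study ends when "279 strokes have occurred or 6,000 study subjects have been followed for at least 36 months".
- Section 10.3: the sample size assumes a median follow-up of 4 years.
- Appendix E, on the device: "It has battery longevity of three years".
- Section 7.2.2 itself says that the national registers record healthcare use continuously.
- Appendix A ticks health economics and QoL at months 12.5, 24.5 and 36.5 in both groups.

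On the utility measurements, section 7.2.2 says EQ-5D-5L is completed "at baseline (before operation) and every second year (mailed to control group"), with scores joined linearly and QALYs taken as the area under the profile. Section 7.2.1 (main study) says: "Assessment of QoL and cognitive function: At randomization, months 12, 24 and 36".

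**The concern.** The two sides of the comparison do not accrue in step. Buying and implanting the device happens once, near randomization, and pays for about three years of monitoring. Any strokes avoided, and the costs and utility losses avoided with them, build up for as long as subjects are followed. A 24-month cut counts all of the first and only part of the second, while the third year is scheduled for both groups and does not enter the stated comparison.

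The EQ-5D-5L conflict bears on the same estimate. On the section 7.2.2 schedule, a two-year QALY rests on two measurements. On the section 7.2.1 and Appendix A schedule it would rest on three, with a fourth at 36 months.

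Cost-effectiveness is one of the three results the project expects to deliver (section 1, Expected results) and is hypothesis b in section 2.5.2. The horizon and the measurement times should therefore be stated once, consistently and with a reason.

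**Working it through.** The protocol gives no figure for the economic analysis other than the 24-month time point, so there is none to reproduce. The check uses the design inputs.

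**Inputs.** ILR arm 1,500 and control arm 4,500 (synopsis, Sample size). Control rate 1% per year and hazard ratio 0.65 (section 10.3), so the ILR rate is 0.65 × 1% = 0.65% per year.

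**Which end-of-study condition comes first.** Section 10.1 joins 36 months to 279 strokes by an *or*.

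- Expected primary events per year: 4,500 × 0.010 + 1,500 × 0.0065 = 45 + 9.75 = 54.75.
- Mean follow-up needed for 279 events: 279 / 54.75 = 5.1 years.
- Events at four years' mean follow-up: 54.75 × 4 = 219 (215 with exponential event times).

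At the planned rates the 36-month condition is met before 279 events. The third year is therefore expected to exist for most subjects, apart from deaths and withdrawals.

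**Primary events avoided in the ILR arm.** Constant hazards, effect from day 0: 1,500 × (0.0100 − 0.0065) × T = 5.25 × T.

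| Horizon | Events avoided | 24-month total as a share |
|---|---|---|
| 24 months | 10.5 | – |
| 36 months | 15.75 | 10.5 / 15.75 = 67% |
| 48 months (assumed median follow-up) | 21.0 | 10.5 / 21.0 = 50% |

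With exponential event times, 1,500 × [exp(−0.0065T) − exp(−0.01T)] gives 10.33 at 24 months and 15.37 at 36, again 67%.

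**Sensitivity (my assumption, not in the protocol).** Section 10.3 expects the 30% AF yield over at least three years of monitoring, so the effect may not be full from day 0. If the hazard difference rises linearly over three years, events avoided up to year 3 are proportional to T²/6. The 24-month share of the 36-month total is then (4/6) / (9/6) = 44%.

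**EQ-5D-5L points.** Section 7.2.2 gives months 0 and 24. If EQ-5D-5L is part of the QoL forms, section 7.2.1 and Appendix A give 0, 12, 24 and 36 (Appendix A shows the visits at 12.5, 24.5 and 36.5).

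**Does two-point interpolation shift the group mean?** Take a lasting utility loss d after a stroke at time U, uniform on 0 to 2 years. The true mean loss by 24 months is d × E(2 − U) = d × 1 = d. A straight line from month 0 to month 24 gives ½ × 2 × d = d. The two agree, so under these assumptions individual losses are mistimed but the group mean is not shifted.

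**The case against.** The strongest reply is that the 24-month sentence does not say later data go unused, that the ICER paragraph names no horizon, and that Appendix A does schedule economic data at 36.5 months. That is fair as far as it goes. But 24 months is the only horizon the section names, so the text at least needs to say what the third year is for.

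The two statements in section 7.2.2 also fit each other. If EQ-5D-5L really is collected every second year, month 24 is the last utility measurement before month 36. This stands, and it means a 36-month QALY is only available at no extra cost if EQ-5D-5L is among the QoL forms in section 7.2.1 and Appendix A. Section 7.2.2 is the only place that names the instrument and gives its timing.

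The 36-month minimum is a plan, not a guarantee: section 10.1 offers 279 strokes as an alternative end, and deaths and withdrawals shorten follow-up.

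A reader might infer that the ICER is biased against ILR. The documents do not support that. The direction presupposes that the hazard ratio of 0.65 is true, which is the trial's hypothesis. Transmission review and yearly visits (section 7.2.1), anticoagulation (7.7) and bleeding (12.1) continue to generate costs and harms after 24 months. A reader might also divide the device prices in Appendix G by strokes avoided, or scale QALY gains by the square of time. The first covers device purchase only and is not an ICER. The second ignores mortality in subjects aged 70 to 90. Nor can it be said that straight-line interpolation biases the mean, as the working shows.

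Finally, costs and QALYs are supplementary endpoints (section 10.2.4), so the primary analysis, error control and subject safety are untouched.

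**Conclusion.** The point holds as a poorly justified horizon and an internal contradiction. Section 7.2.2 bases the cost and QALY differences on 24 months without a reason, while the planned follow-up, the device's working life and the scheduled data all reach 36 months. If the design assumptions hold, 24 months captures about two-thirds of the primary events avoided by 36 months (10.5 against 15.75 per 1,500). This rests on constant hazards and a full effect from day 0; a gradual build-up would lower the share. The consequence for the ICER is not quantified in size or direction. Separately, the EQ-5D-5L timing in section 7.2.2 disagrees with the QoL timing in section 7.2.1 and Appendix A and must be reconciled whichever horizon is kept. The point deserves correction because it concerns one of the project's three expected results.

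**What to change.** In section 7.2.2:

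1. Set the main within-trial horizon for costs, QALYs and the ICER at 36 months, and keep 24 months as a sensitivity analysis.
2. Replace the every-second-year EQ-5D-5L schedule by baseline and months 12, 24 and 36, matching section 7.2.1 and Appendix A, and use all of these points in the area under the utility profile.
3. Confirm in section 7.2.1 and Appendix A that EQ-5D-5L is one of the QoL forms at those time points in both groups.

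**Cost.** Mostly text and analysis work, because register costs are continuous and the QoL and economic assessments are already scheduled. There will be somewhat more missing or censored data at month 36, and a discount rate must be named. If EQ-5D-5L turns out not to be in the scheduled QoL forms, it must be added at months 12 and 36; the control group would then need additional mailed questionnaires.
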